6.3 STUDY POPULATION

Inclusion criteria:

- Patient has two or more documented clinical visits in the National Anti-Tumor Drug Surveillance System (NATDSS) network on or after January 1, 2013.
- Patient has a confirmed diagnosis of DDLPS during his/her lifetime.
- At least 18 years old at the date of initial diagnosis

No exclusion criteria are applied.

Eligible population will be divided into two groups:

- Cohort 1 will include unresectable locally advanced or metastatic DDLPS patients who received at least one line of systemic antineoplastic treatment by the end of cohort identification period (index date = start date of first line (1L) treatment).
- Cohort 2 will include patients with DDLPS who have not initiated 1L systemic antineoplastic treatment by the end of cohort identification period (index date = date of initial DDLPS diagnosis during cohort identification period). Patients initiated 1L treatment afterwards or patients received adjuvant and/or neoadjuvant therapy only through follow-up will be included in Cohort 2.

In both cohorts, 1L therapy will be defined as the initial set of drugs used after unresectable locally advanced or metastatic diagnosis. Metastatic patients will be defined as those with metastatic diagnosis or presence of metastatic sites; unresectable locally advanced patients will be defined as those with advanced diagnosis and without subsequent surgical resection.

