7.1.2 Secondary outcomes

Survival after initial diagnosis

Outcome type: Secondary

• Outcome name: Survival after initial diagnosis

• **Time frame**: Time from initial diagnosis until the earliest record of death or end of the study period

• **Population**: Cohort 1, Cohort 2

Survival after initial diagnosis for each patient will be defined as the date of death minus the date of initial diagnosis. For patients with no record of death, survival after initial diagnosis will be censored at the last activity date before the end of the study period.

Description of treatment patterns

Outcome type: Secondary

• Outcome name: Treatment patterns

• Time frame: Treatment patterns are assessed at the index date and during follow-up

■ **Population**: Cohort 1, Cohort 2

The following variables of interest will be assessed to describe treatment patterns defined by LOT and regimens.

Treatment patterns by LOT and regimens

Variable	Definition	Timing
1L Treatment Type	Regimen name from LOT data for treatments with line number = 1, 2 and 3. Treatment	Any time after
2L Treatment Type	types will be classified as follows, specific treatments and categories may change upon examination of the data:	index date
3L Treatment Type		

Statistical and Epidemiological Analysis Plan (SEAP) for Observational and Non-Interventional Studies (ONIS)

[figure not shown]
Variable	Definition	Timing
	NCCN/CSCO preferred	
	 Doxorubicin 	
	 Epirubicin 	
	 Liposomal doxorubicin 	
	AD (doxorubicin, dacarbazine)	
	 AIM (doxorubicin, ifosfamide, mesna) 	
	Ifosfamide, epirubicin, mesna	
	 Larotrectinib (NTRK fusion pos sarcomas only) 	
	 Entrectinib (NTRK fusion pos sarcomas only) 	
	 Pazopanib 	
	• Eribulin	
	Trabectedin	
	Other	
	 AD LMS only (doxorubicin, dacarbazine) 	
	Gemcitabine and docetaxel	
	Gemcitabine	
	Gemcitabine and vinorelbine	
	Gemcitabine and dacarbazine	
	 Dacarbazine 	
	 Ifosfamide 	
	Temozolomide	
	Vinorelbine	
	 Regorafenib 	
	 MAID (mesna, doxorubicin, ifosfamide, dacarbazine) 	
	 Pembrolizumab 	
	 durvalumab 	
	• Other	
Total number of treatment lines	From LOT data, for all lines after index date, categorical variable defined as total of treatment lines reported.	Any time after index date
Concurrent steroid therapy	Any record of a drug classified as a corticosteroid.	Anytime from the start to end of 1L, 2L, or 3L

Statistical and Epidemiological Analysis Plan (SEAP) for Observational and Non-Interventional Studies (ONIS)

Page 9 of 36

Variable	Definition	Timing

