10.1.2 Analysis of secondary objectives

Survival after initial diagnosis will be estimated by the KM method to obtain median estimates with 95% CIs and IORs for Cohort 1 and Cohort 2.

Treatment patterns for Cohort 1 and Cohort 2 will be described by the number of lines, count with percentage (%) of patients by treatment lines, type of therapy and therapy regimens in each line.

LOTs are defined by the temporal relationship and sequencing of treatment regimens by using the dates of initiation and discontinuation of chemotherapy, targeted therapy, and/or immunotherapy. For each patient, 1L treatment regimen is defined as the first systemic treatment of any chemotherapy, and/or targeted drugs given to a patient after advanced or metastatic DDLPS diagnosis. A treatment line is advanced to the next line when a patient initiates new combinations of drugs or has the evidence of progression of disease. The start date of each LOT is defined as the date of initiation of new regimen, and the end date of each LOT is defined as the date of last dose prescribed or recorded at/before discontinuation.

Statistical and Epidemiological Analysis Plan (SEAP) for Observational and Non-Interventional Studies (ONIS)

Page 18 of 36

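### SAP 10.1.2 leaves immunotherapy out of its first-line definition, in conflict with its own line rule, SAP 6.3 and Protocol 9.2.2; applied literally, it would mislabel immunotherapy-first patients in the treatment-pattern tables

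*SAP*

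**What the plan says.** SAP 10.1.2 governs the analysis of treatment patterns, a secondary outcome, which are to be "described by the number of lines, count with percentage (%) of patients by treatment lines, type of therapy and therapy regimens in each line". It first says that lines are derived "by using the dates of initiation and discontinuation of chemotherapy, targeted therapy, and/or immunotherapy". The next sentence narrows this for the first line: "1L treatment regimen is defined as the first systemic treatment of any chemotherapy, and/or targeted drugs given to a patient after advanced or metastatic" (the diagnosis follows).

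SAP 6.3 defines the same term for both cohorts without naming drug classes: "1L therapy will be defined as the initial set of drugs used after unresectable locally advanced or metastatic diagnosis". Protocol 9.2.2 uses identical wording. Cohort 1 patients are those who "received at least one line of systemic antineoplastic treatment by the end of cohort identification period"; Cohort 2 patients are those who "have not initiated 1L systemic antineoplastic treatment by the end of cohort identification period".

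In SAP 7.1.2 the treatment-type variable is "Regimen name from LOT data for treatments with line number = 1, 2 and 3", and the number of lines is "From LOT data, for all lines after index date, categorical variable defined as total of treatment lines reported". One regimen list serves 1L, 2L and 3L. It includes pembrolizumab and durvalumab, and both reappear as rows in mock Table 6, which has 1L, 2L and 3L columns.

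**The concern.** Two incompatible 1L rules stand in the same SAP. The conflict cannot be removed by reading immunotherapy into targeted drugs, because the preceding sentence of SAP 10.1.2 lists targeted therapy and immunotherapy as separate classes. Protocol 9.7 leaves full analysis detail to this plan, and SAP 10.1.2 is the only visible text that says how lines are built, advanced, started and ended. An analyst numbering lines would therefore work from that paragraph, and a second analyst checking the work could code the other rule and also cite the SAP.

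At stake are the regimen-by-line results. The patients affected are those whose first systemic treatment after advanced diagnosis is immunotherapy alone. Patients who start immunotherapy together with chemotherapy or a targeted drug have the same 1L start date under either rule.

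**Working it through.** The plan states no figure for this point, so there is nothing to reproduce. The check is a comparison of definitions, one count, and a bound.

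**1. The definitions side by side**

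| Place | Classes that count as 1L |
|---|---|
| SAP 10.1.2, 1L sentence | Chemotherapy and/or targeted drugs |
| SAP 10.1.2, preceding line rule | Chemotherapy, targeted therapy and/or immunotherapy (any line) |
| SAP 6.3 and Protocol 9.2.2 | No class limit |
| SAP 7.1.2 list and Table 6 | Pembrolizumab and durvalumab are listed for 1L to 3L |

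Only the first row leaves immunotherapy out.

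**2. One hypothetical patient.** After advanced diagnosis the patient receives pembrolizumab alone, then doxorubicin. Under SAP 6.3, 1L is pembrolizumab and 2L is doxorubicin. Under the SAP 10.1.2 sentence, 1L is doxorubicin and pembrolizumab has no defined line number.

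**3. Rows affected by rule.** The list has 11 preferred regimens and 13 named other regimens: 11 + 13 = 24. Two of them, pembrolizumab and durvalumab, are immunotherapy given alone. Under the literal sentence these 2 of 24 rows must be zero in the 1L columns, whatever the data show.

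**4. Possible size.** Neither of the following inputs is in the documents; both are assumptions.

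- p = share of treated patients whose first systemic treatment is immunotherapy alone.
- s = share of those patients who later start chemotherapy or a targeted drug.

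Under the literal sentence, the share of reported 1L regimens that are truly second-line is ps / (1 − p + ps). This cannot exceed p: the inequality reduces to s(1 − p) ≤ 1 − p, which is true for every s up to 1. A share p(1 − s) of treated patients would have no 1L regimen to report.

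With s = 0.5:

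- p = 1%: 0.005 / 0.995 = 0.5% truly second-line; 0.01 × 0.5 = 0.5% with no 1L.
- p = 5%: 0.025 / 0.975 = 2.6%; 0.05 × 0.5 = 2.5%.
- p = 10%: 0.05 / 0.95 = 5.3%; 0.10 × 0.5 = 5.0%.

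For s from 0.25 to 1, the truly second-line share runs from 0.25% to 1.00% (p = 1%), 1.30% to 5.00% (p = 5%) and 2.70% to 10.00% (p = 10%). If p is near zero, both shares are near zero.

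**The case against.** The strongest reply is that the intent is plain. The preceding sentence, SAP 6.3, Protocol 9.2.2 and the regimen list all point the same way, and one sentence is the outlier. SAP 11 has the study lead verify that the analyst follows the protocol's methodology, and SAP 9.2 has medical experts review the data transformation rules. This stands in part: it makes literal use less likely and makes the omission look like a slip. It does not correct the sentence, which sits in the one paragraph that sets out how lines are built. Parts of the SAP are blacked out, so it can only be said that no visible text resolves the conflict.

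A reader might infer three stronger consequences, and the documents do not support them.

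- *That Table 5 (number of lines) and Table 6 (regimen by line) would contradict each other.* SAP 7.1.2 takes both variables from the same line-of-therapy data. They disagree only if the broad rule is used for one table and the narrow rule for the other, and no text prescribes that.
- *That immunotherapy-only patients would have no clear cohort, or that the index date and primary OS would shift.* SAP 6.3 sets cohort entry and 1L for both cohorts without a class limit, and the Cohort 1 index date is the start of that 1L. A shift needs the SAP 10.1.2 sentence to override SAP 6.3, which nothing says.
- *That the subgroup with doxorubicin as 1L must be mislabelled.* That subgroup is stated in Protocol 9.7.4, and the protocol's only visible 1L definition is the unrestricted one.

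**Conclusion.** The inconsistency is real and should be corrected, because the two rules give different regimen-by-line tables for a secondary outcome. The established consequence is conditional. If the SAP 10.1.2 sentence is applied as written, 1L immunotherapy monotherapy cannot appear in the treatment-pattern tables, and an immunotherapy-first patient's later chemotherapy or targeted regimen is reported as 1L. OS by line and 1L-defined subgroups, which are planned only if feasible, would be affected only if they use that sentence. No effect on cohort assignment, index date or primary OS is shown.

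The size is unknown. The shares in the calculation illustrate assumed values of p and s and are not estimates for this database; the true effect may be negligible. The row count and the bound by p need no assumption about how common immunotherapy-first treatment is.

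**What to change.** In SAP 10.1.2, replace the 1L sentence with a reference to the definition in SAP 6.3 and Protocol 9.2.2, with its scope spelled out: the initial set of systemic antineoplastic drugs (chemotherapy, targeted therapy and/or immunotherapy) used after unresectable locally advanced or metastatic diagnosis. Add that this single definition is used for line numbering, index date, cohort assignment and 1L-defined subgroups.

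The reference also removes a smaller difference: SAP 10.1.2 starts the clock at advanced or metastatic diagnosis, whereas SAP 6.3 and Protocol 9.2.2 require locally advanced disease to be unresectable.

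The cost is a short wording change in the SAP. No new data are needed and the mock tables stay as they are.

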9.2.2. Study population

Inclusion criteria:

- Patient has two or more documented clinical visits in the National Anti-Tumor Drug Surveillance System (NATDSS) network on or after January 1, 2013.
- Patient has a confirmed diagnosis of DDLPS during his/her lifetime.
- At least 18 years old at the date of initial diagnosis

No exclusion criteria are applied.

Eligible population will be divided into two groups:

NIS Protocol BI Study Number 1403-0024

Page 13 of 37 C42272174

Proprietary confidential information© 2023 Boehringer Ingelheim GmbH or one or more of its affiliated companies

- Cohort 1 will include unresectable locally advanced or metastatic DDLPS patients who received at least one line of systemic antineoplastic treatment by the end of cohort identification period (index date = start date of 1L treatment).
- Cohort 2 will include patients with DDLPS who have not initiated 1L systemic antineoplastic treatment by the end of cohort identification period (index date = date of initial DDLPS diagnosis during cohort identification period). Patients initiated 1L treatment afterwards or patients received adjuvant and/or neoadjuvant therapy only through follow-up will be included in Cohort 2.

In both cohorts, 1L therapy will be defined as the initial set of drugs used after unresectable locally advanced or metastatic diagnosis. Metastatic patients will be defined as those with metastatic diagnosis or presence of metastatic sites; unresectable locally advanced patients will be defined as those with advanced diagnosis and without subsequent surgical resection.

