10.1 MAIN ANALYSIS

10.1.1 Analysis of primary objective

OS will be analyzed for Cohort 1. For OS calculation, the event time is the date of death recorded by the National Mortality Database from CDC. OS is defined as the time from initiation of 1L until the date of death due to any cause. Patients without death record during the study period will be censored at the last medical record during the study period.

OS will be estimated by the KM method to obtain median estimates with 95% CIs and IQRs for Cohort 1, calculated using the log-log transformation. OS rate at 6, 12, 18, and 24 months will be described according to the survival curves if reached.

OS may be assessed by LOT and type of treatment received in each LOT, pending feasibility. OS by LOT is defined as the time from initiation of each LOT until the date of death due to any cause.

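### SAP 10.1.2 omits the unresectable condition from its first-line (1L) definition; programmed as written, it would count perioperative drugs as 1L in resected patients who later relapse and start primary OS too early

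*SAP*

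**What the plan says.** Two definitions of 1L stand in the SAP.

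- SAP 6.3, matching Protocol 9.2.2: "In both cohorts, 1L therapy will be defined as the initial set of drugs used after unresectable locally advanced or metastatic diagnosis".
- SAP 10.1.2, which sets the rules for opening, advancing and closing lines: the first chemotherapy and/or targeted drug "given to a patient after advanced or metastatic DDLPS diagnosis".

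SAP 6.3 also defines the terms. On local disease: "unresectable locally advanced patients will be defined as those with advanced diagnosis and without subsequent surgical resection". On metastatic disease: "Metastatic patients will be defined as those with metastatic diagnosis or presence of metastatic sites", with no limit on when the metastasis appears.

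The visible text on perioperative therapy is one sentence in the Cohort 2 definition: "Patients initiated 1L treatment afterwards or patients received adjuvant and/or neoadjuvant therapy only through follow-up will be included in Cohort 2".

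The Cohort 1 index date (SAP 6.4) is the start of 1L, and so is the origin of the primary outcome in SAP 10.1.1: "OS is defined as the time from initiation of 1L until the date of death due to any cause".

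**The concern.** Under SAP 6.3, unresectable means an advanced diagnosis with no later resection. An advanced diagnosis without that condition therefore includes patients who were later operated on. SAP 10.1.2 drops the condition.

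This matters for a patient with locally advanced disease who receives perioperative drugs, is resected, and later metastasises and is treated again. That patient belongs in Cohort 1 as metastatic. Under SAP 6.3, 1L is the treatment given after the metastasis. Under a literal reading of SAP 10.1.2, it is the perioperative course.

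Index date, primary OS, OS by line, regimen by line, and the Table 2 item on surgeries before 1L all depend on that date. An early date puts a perioperative course and the interval before relapse into survival from 1L, time the patient had to survive in order to reach relapse treatment. It also moves the relapse regimen into the second-line column. Protocol section 7 says the authority recommended collecting these data to support a New Drug Application, and Protocol section 12 says they may supplement regulatory submissions.

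**Working it through.** **1. One patient under both definitions (constructed example).** Locally advanced diagnosis January 2015; neoadjuvant chemotherapy February 2015; resection June 2015; lung metastases January 2018; systemic therapy February 2018; death December 2018.

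| | SAP 6.3 / Protocol 9.2.2 | SAP 10.1.2 as written |
|---|---|---|
| 1L starts | February 2018 | February 2015 |
| OS | 10 months | 46 months |
| February 2018 regimen is | first line | second line |

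With adjuvant drugs instead, the 10.1.2 clock would start after the operation but still before the relapse.

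**2. Does the perioperative sentence resolve it?** It covers patients whose only therapy was perioperative, so it does not cover this one. It also creates a cohort conflict. A patient who had perioperative drugs, then metastasised, and received no further systemic therapy is in Cohort 1 under 10.1.2 and in Cohort 2 under the 6.3 sentence.

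**3. The plan's own precision figures.** Protocol 9.5 assumes exponential survival with a median of 8, 10 or 12 months, uniform enrolment and about 20% censoring. With uniform censoring on (0, T), 20% censored requires λT = 4.965. The Kaplan-Meier variance term at the median is V = ∫₀^ln2 eᵘ/(1 − u/4.965) du = 1.086, and the log-log interval is median × exp(±1.96·√V/(ln2·√N)). For N = 500 and median 10 this gives 8.765 to 11.409, against the printed 8.754 to 11.378. All 12 rows agree within 0.52%. The table is not in dispute and serves only as a yardstick.

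**4. Possible size.** The documents give neither the affected share f of Cohort 1 nor the lead time L from perioperative start to true 1L. Both are assumed. With λ = ln2/10 = 0.0693 per month and L uniform on 6 to 36 months, for t between 6 and 36:

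S(t) = (1 − f)·e^(−λt) + f·[(36 − t)/30 + (1 − e^(−λ(t−6)))/(30λ)]

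For f = 10% at t = 11.59: 0.9 × 0.4478 + 0.1 × (0.8137 + 0.1545) = 0.4030 + 0.0968 = 0.500, so the median is 11.59 months. Solving for the other shares:

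| f | Median (true value 10) | 24-month OS |
|---|---|---|
| 0% | 10.00 | 18.9% |
| 1% | 10.14 | 19.5% |
| 2% | 10.29 | 20.0% |
| 5% | 10.74 | 21.7% |
| 10% | 11.59 | 24.5% |
| 20% | 13.62 | 30.0% |

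At f = 5%, 10% and 20% the same formula gives 8.61, 9.32 and 11.08 months for a true median of 8, and 12.86, 13.82 and 16.07 for a true median of 12.

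A fixed short lead matters less: L = 6 months and f = 5% moves 10 to 10.37. A fixed L = 12 with f = 10% gives 11.70.

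**5. Against the precision table.** At f = 10%, 11.59 lies above the N = 500 upper limit (11.378) but below the N = 300 limit (11.814). The documents do not state an expected N.

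**The case against.** The strongest reply is that SAP 6.3 governs and 10.1.2 is shorthand. SAP 6.3 is the population section; it defines Cohort 1, its index date and 1L for both cohorts, and the protocol carries only that definition. SAP section 11 has the study lead check that the analyst followed the protocol's methodology. Cohort 2 consists of patients who have not started 1L by the end of the identification period, so placing perioperative-only patients there shows that such therapy was not meant to count as 1L. Protocol section 7 also uses advanced DDLPS, without further qualification, for the first-line setting.

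Most of this stands, and it makes the intent clear. It does not remove the conflict. SAP 10.1.2 is where the line rules are written, SAP 6.3 itself treats an advanced diagnosis as the broader category, and no visible text ranks the two. An analyst who coded 10.1.2 literally would be following the SAP.

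Two further limits stand. The exploratory variable-definition pages and the text between SAP 10.1.2 and 10.3 are not visible, so a perioperative rule may exist there. The affected share may also be small, since a patient needs an advanced diagnosis before the perioperative drugs, then a resection, then a relapse.

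A reader might infer that the plan as written biases primary OS, or that the clock always starts before the operation. The documents support neither. The early clock arises only if 10.1.2 is programmed in place of 6.3, and a start before surgery applies only to neoadjuvant drugs.

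**Conclusion.** The SAP contains two conflicting definitions of the date that starts the primary outcome, and they should be reconciled before the index date is programmed. For each affected patient, following 10.1.2 can only lengthen measured OS. That is the same direction as the over-estimation Protocol 9.9 already expects from incomplete death capture.

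The size cannot be derived from the documents. Under the assumed 10-month exponential median and uniform 6-to-36-month lead, the shift runs from about 0.1 month at 1% affected to about 3.6 months at 20%. A reader might infer that the bias would exceed the planned sampling error. That depends on an unstated N and an assumed share: at 10% affected it holds for N = 500 and fails for N = 300. The reason to act is that time zero is ambiguous and cheap to settle, not that a bias of known size has been shown.

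**What to change.** Replace the 1L wording in SAP 10.1.2 with the SAP 6.3 / Protocol 9.2.2 definition, and use that single definition for index date, OS, OS by line and regimen by line.

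Because SAP 6.3 identifies unresectable disease only in retrospect, by the absence of later surgery, add dating rules to the line derivation:

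- Systemic drugs given around a resection, before any metastatic diagnosis and before any later unresectable relapse, do not open 1L or set the index date.
- For a resected patient who relapses, with metastases or with locally advanced disease not resected again, 1L is the first systemic drug on or after the date of that relapse diagnosis.
- For a locally advanced patient who is never resected, 1L is the first systemic drug on or after the advanced diagnosis date.

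Report the share of Cohort 1 with prior perioperative therapy.

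The cost is SAP wording and a little programming with surgery and diagnosis dates, which the cohort definitions already require. The reported median may be shorter than under a literal 10.1.2.
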